### 3.1.1 Dose Limiting Toxicity

DLT will be defined as any grade  $\geq 3$  adverse event which is thought to be probably or definitely related to the investigational drug. Grade 3 toxicities that resolve within 72 hours to  $\leq$  grade 1 with supportive care (e.g. pruritus, nausea, vomiting, fatigue, diarrhea) will not be counted as DLTs. Study drug and placebo will be held until resolution of any grade  $\geq 3$  adverse event. If 2 subjects experience a grade 3 AE probably or definitely attributable to the study drug, the study will be stopped for safety review. In patients that have experienced disease progression, further dosing will cease in a patient at the occurrence of the first DLT. All patients will be evaluable for toxicity from the time of their first treatment with topical ruxolitinib until the end of study participation, regardless of inclusion in primary response evaluation.

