### **3 STUDY IMPLEMENTATION**

#### **3.1 STUDY DESIGN**

This is a phase II, placebo controlled study to evaluate the safety, tolerability, and efficacy of 1.5% topical ruxolitinib cream, INCB018424, in patients with epidermal cGVHD. Case series and anecdotal reports of systemic JAK inhibitors in cGVHD have suggested a benefit for cGVHD involvement of the skin and other organs, warranting further study. For patients with cGVHD that manifests with primarily epidermal skin disease, effective topical therapy is desirable. Current topical therapies (corticosteroids and calcineurin inhibitors), can have significant side effects and are not specific to the disease pathology.

In this study, patients with a minimum of 2 distinct areas of involvement with intact (no ulceration) epidermal cGVHD that has been confirmed histologically, will be eligible for participation. Each participant will receive active study agent and placebo. Chronic GVHD is a heterogeneous disease with a waxing and waning course. Given the heterogeneity and the natural history of this disease as well as use of concurrent systemic medications, each participant will serve as his/her own control to allow for better comparison of placebo and active study drug. Randomization table generated by [name], statistician, will be provided to the pharmacy, such that the labeling of placebo and active study drug as container A and B will be randomized at the pharmacy. All participants will be provided with active study drug to apply to the designated affected area (maximum application BSA of 10%) twice a day and a second container containing a vehicle cream to be applied twice a day on a second affected area. Subjects who experience dose limiting toxicities (DLT) will have the dose adjusted as described in Section 3.1.1.

**Abbreviated Title:** Topical ruxolitinib in cGVHD

**Version Date:** 01/25/2021

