### 3.3 DOSE MODIFICATIONS

**Table 1: Dose Modifications**

All dose modifications will be discussed with the PI or MAI.

Adverse event	CTCAE grade/attribution	Protocol Action
Any adverse event (excluding ulceration, infection, treatment-related malignancy)	Grade 2 >7 days that is probably or definitely related to study drug.	Hold study drug; *If AE resolves to ≤ grade 1 or baseline within 7 days: resume dose. ** If AE does not resolve to ≤ grade 1 or baseline within 7 days: patient comes off drug.
Any adverse event (excluding ulceration, infection, treatment-related malignancy)	Same grade 2 >7 days recurs that is probably or definitely related to study drug.	Hold study drug; *If AE resolves to ≤ grade 1 or baseline within 7 days: decrease dose to once daily. **If AE does not resolve to ≤ grade 1 or baseline within 7 days: patient comes off drug.
Any adverse event (excluding ulceration, infection, treatment-related malignancy)	Same grade 2 >7 days recurs after dose reduction that is probably or definitely related to study drug.	Patient comes off drug.
Any adverse event (excluding ulceration,	Grade 3 that is probably or definitely related to study drug.	Hold study drug; *If AE resolves to ≤ grade 1 or baseline within 7 days:

**Abbreviated Title:** Topical ruxolitinib in cGVHD

**Version Date:** 01/25/2021

infection, treatment-related malignancy)		decrease dose to once daily. **If AE does not resolve to $\leq$ grade 1 or baseline within 7 days: patient comes off drug.
Any adverse event (excluding ulceration, infection, treatment-related malignancy)	Same grade 3 recurs after dose reduction that is probably or definitely related to study drug.	Patient comes off drug.
Any adverse event (excluding ulceration, infection, treatment-related malignancy)	Grade 4 that is probably or definitely related to study drug.	Patient comes off drug.
Skin ulceration at treatment site	Any grade	Patient comes off drug.
Infection	Grade 2 that is probably or definitely related to study drug.	Hold study drug until completion of systemic antibiotic course and resolution of infection, then restart at same dose level.
Infection	Grade 2 recurs that is probably or definitely related to study drug.	Hold study drug until completion of systemic antibiotic course and resolution of infection, then decrease dose to once daily.
Infection	Grade 2 recurs after dose reduction that is probably or definitely related to study drug.	Patient comes off drug.

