#### **7.5 IND SPONSOR REPORTING CRITERIA**

An investigator must immediately report to the sponsor, using the mandatory MedWatch form 3500a or equivalent, any serious adverse event, whether or not considered drug related, including those listed in the protocol or investigator brochure and must include an assessment of whether there is a reasonable possibility that the drug caused the event.

- All Grade 5 (fatal) events (except death due to progressive disease) must be reported via email within 24 hours. A complete report must be submitted within one business day.
- All other serious adverse events including deaths due to progressive disease must be reported within one business day

Study endpoints that are serious adverse events (e.g. all-cause mortality) must be reported in accordance with the protocol unless there is evidence suggesting a causal relationship between the drug and the event (e.g. death from anaphylaxis). In that case, the investigator must immediately report the death to the sponsor.

Events will be submitted to PI and study coordinator.

Events will be submitted to [REDACTED], authorized representative for the IND Sponsor (NIAMS) at:

**Abbreviated Title:** Topical ruxolitinib in cGVHD

**Version Date:** 01/25/2021

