## **7.7 DATA AND SAFETY MONITORING PLAN**

### **7.7.1 Principal Investigator/Research Team**

The clinical research team will meet on a biweekly basis when patients are being actively treated on the trial to discuss each patient. Decisions about dose level enrollment and dose escalation if applicable will be made based on the toxicity data from prior patients.

All data will be collected in a timely manner and reviewed by the principal investigator or the medical advisory investigator. Adverse events will be reported as required above. Any safety concerns, new information that might affect either the ethical and or scientific conduct of the trial, or protocol deviations will be immediately reported to the IRB using iRIS and to the Sponsor.

The principal investigator will review adverse event and response data on each patient to ensure safety and data accuracy. The principal investigator will personally conduct or supervise the investigation and provide appropriate delegation of responsibilities to other members of the research staff.

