#### **8.4.4 Safety Analyses**

Safety of the agent will be assessed by reporting the grade of adverse events noted in each patient, and reporting the fraction with grade 3 and grade 4 adverse events. Safety data will be presented in individual listings. Summaries will also be prepared. The safety data will consist of the reporting of all adverse events, vital signs, physical examination data, and appropriate laboratory safety data.

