### 11.1.2 Toxicity

Topical ruxolitinib has been evaluated in over 2350 subjects in at least 17 clinical studies in healthy volunteers and participants with psoriasis, atopic dermatitis, alopecia areata and vitiligo for a duration of 1-26 months.

There have been no treatment related deaths. To date, only one severe, and/or life-threatening treatment emergent adverse event (TEAE), dermatitis atopic, has been attributed to the study drug. All other SAEs were considered unlikely related or unrelated to study drug.

Other TEAEs that led to discontinuation of topical ruxolitinib include mild to moderate occurrences of application site irritation, a Grade 3 elevation in GGT, headache, fatigue, nausea, atopic dermatitis and hypertriglyceridemia.

In an ongoing study of atopic dermatitis, a total of 67 pediatric participants (aged 2 to 17 years) received ruxolitinib cream 0.5%, 1.5%, or 0.75% cream BID. No participant had a fatal TEAE, SAE, or TEAE leading to discontinuation of ruxolitinib cream.

Cutaneous AEs were seen with similar frequency for vehicle-treated lesions and active comparator treated lesions when compared with topical ruxolitinib treated lesions.

The most common AEs that were considered possibly related to the study drug include transient hypoesthesia, transient leukopenia and reticulocytosis, pruritus, upper respiratory infections, nasopharyngitis, headache, acne, dermatitis atopic, and transient application site irritation. All were considered mild to moderate and resolved with or without the need for concomitant medications.

Oral ruxolitinib is FDA approved for treatment of myelofibrosis and polycythemia vera in adults. The most common AEs with oral administration include thrombocytopenia, anemia, neutropenia, infection, nonmelanoma skin cancer, elevation of AST and ALT. Systemic exposure with topical ruxolitinib is several fold below the doses that are associated with AEs following oral dosing.

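### The study-level safety stop in 3.1.1 counts grade 3 events where it should count grade ≥3, so read literally two related grade 4 or 5 events do not trigger it

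*Combined protocol and SAP*

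**What the plan says.** Section 3.1.1 sets several thresholds in one paragraph:

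- A DLT is any adverse event of grade ≥3 that is probably or definitely related to the drug.
- Grade 3 toxicities that settle to grade ≤1 within 72 hours with supportive care do not count as DLTs.
- The hold covers both creams: "Study drug and placebo will be held until resolution of any grade", followed by ≥3.
- The study-level stop reads: "If 2 subjects experience a grade 3 AE probably or definitely attributable to the study drug, the study will be stopped for safety review".

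Elsewhere grade 4 is kept apart from grade 3. For general adverse events, Table 1 (Section 3.3) has a related grade 3 event lead to a hold and, if it resolves within 7 days, once-daily dosing. A separate row, "Grade 4 that is probably or definitely related to study drug", takes the patient off drug. Section 8.4.4 plans on "reporting the fraction with grade 3 and grade 4 adverse events".

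**The concern.** The stop sentence carries no ≥ sign and does not say or higher, while the DLT and hold sentences beside it both use ≥3. If the words mean what they say, the rule that obliges the team to stop for safety review does not respond to the most serious related events.

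Safety and tolerability is a primary objective, patients may be as young as 12, and Section 1.2.3 notes that cGVHD patients may have baseline cytopenias and little reserve. If the mandatory stop does not fire, pausing treatment and enrolment for the other patients is left to judgement.

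**Working it through.** **1. Does a bare grade 3 mean exactly grade 3 here?**

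- In the same paragraph, the 72-hour exception is written for grade 3 and plainly does not extend to grade 4.
- Where the paragraph means 3 and above, it uses the ≥ sign, twice.
- Table 1 gives grades 3 and 4 separate rows for general adverse events, infection and treatment-related malignancy.

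So the literal reading is the ordinary one.

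**2. What the two wordings count** (each subject counted once, at the highest grade; 2 are needed to stop)

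| Related events | Counted as written | Counted with ≥3 |
|---|---|---|
| Two subjects, grade 3 | 2, stop | 2, stop |
| One grade 3, one grade 4 | 1, no stop | 2, stop |
| Two subjects, grade 4 or 5 | 0, no stop | 2, stop |

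**3. Does another rule fill the gap?** Table 1 and 3.8.1 act on the individual patient. Sections 7.5 and 7.7.1 require reporting and team review without a count. Section 8.4.6 plans no interim analysis. No other numeric study-level stop was found.

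**4. Size.** The plan gives no operating characteristics for the stop, so there is no figure of its own to reproduce.

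Inputs:

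- n = 15, the accrual ceiling in Section 8.2.
- A stop needs 2 affected subjects (Section 3.1.1).
- The per-patient rate p of related events is assumed, because the documents give none for topical ruxolitinib in cGVHD.

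Formula: P(stop) = 1 − (1−p)^15 − 15p(1−p)^14.

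| p | (1−p)^15 | 15p(1−p)^14 | P(stop) |
|---|---|---|---|
| 0.01 | 0.8601 | 0.1303 | 0.0096 |
| 0.05 | 0.4633 | 0.3658 | 0.171 |
| 0.10 | 0.2059 | 0.3432 | 0.451 |
| 0.20 | 0.0352 | 0.1319 | 0.833 |

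As written, p is the rate of subjects whose worst related event is grade 3. With ≥3, p is the rate for grades 3 to 5 together.

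| Assumed grade 3 rate | Assumed grade 4–5 rate | As written | With ≥3 |
|---|---|---|---|
| 0% | 10% | 0 | 0.45 |
| 0% | 20% | 0 | 0.83 |
| 5% | 5% | 0.17 | 0.45 |
| 10% | 5% | 0.45 | 0.68 |
| 5% | 1% | 0.17 | 0.23 |
| 10% | 1% | 0.45 | 0.50 |
| 10% | 0% | 0.45 | 0.45 |

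**5. Anchor from the documents.** Section 11.1.2 says "To date, only one severe, and/or life-threatening treatment emergent adverse event (TEAE), dermatitis atopic, has been attributed to the study drug", among over 2350 subjects, none described as having cGVHD. With p = 1/2350, P(stop) under ≥3 is about 105 × (1/2350)² = 1.9 × 10⁻⁵, or 2 in 100,000.

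**The case against.** The strongest reply is that this is a drafting slip with obvious intent. The same paragraph defines a DLT at grade ≥3, and no sensible team would see two related grade 4 events and carry on because the sentence says grade 3.

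Other safeguards are real:

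- Under 7.5, "An investigator must immediately report to the sponsor, using the mandatory MedWatch form 3500a or equivalent, any serious adverse event", and fatal events other than death from progressive disease are reported within 24 hours.
- Under 7.7.1, safety concerns go immediately to the IRB and the sponsor, and the team meets biweekly.
- A related grade 4 event takes that patient off drug.
- At about 1 patient per month and 6 weeks of treatment, roughly 1.4 patients (6 weeks ÷ 4.33 weeks per month) are on treatment at once, so few others are exposed at any moment.

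The probabilities rest on assumed rates. The zero requires that all severe related events be grade 4–5, and that each subject count only at the highest grade. The protocol states no counting rule, so an event that passed through grade 3 before worsening might arguably count. Where grade 3 dominates, the difference is small, as the 1% rows show.

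Most of this stands. It lowers the chance of harm and limits what the figures can show. It does not supply the missing trigger: the safeguards ensure that events are seen and reported, but none obliges a stop. Nor does a symbol lost in reading the PDF look likely, since the other ≥ and ≤ signs in the paragraph survive and the stop sentence has no gap.

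**Conclusion.** The concern holds. The threshold in the protocol's only numeric study-level stop conflicts with the thresholds beside it, and taken literally it excludes events worse than those it counts. That finding rests on the wording alone, not on any assumed rate.

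The practical size depends on toxicity that the documents do not quantify. With 15 patients, the loss in stopping probability runs from nothing, when all related severe events are grade 3, to 83 percentage points, when 20% of patients have related events and all are grade 4–5. At the past topical rate the rule would almost never fire under either wording. The gap therefore matters only if toxicity in cGVHD is much higher, which is the case a stopping rule exists to cover. Because the rule is a safety obligation and the correction is nearly free, it should be made.

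Counting brief grade 3 events towards the stop is a legitimate cautious choice and is not criticised.

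**What to change.** In the 3.1.1 stop sentence, replace grade 3 with grade ≥3 and leave the rest unchanged. Brief grade 3 events then still count. Using the term DLT instead would also set the grade at ≥3, but would bring in the 72-hour exclusion and make the stop less cautious.

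Three tidy-ups could go in the same amendment; the main point does not depend on them:

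- **Cross-references.** Section 3.1 says "Subjects who experience dose limiting toxicities (DLT) will have the dose adjusted as described in Section 3.1.1", but the reduction steps are in Table 1. Section 3.8.1 cites 11.1.2 for a definition of unacceptable toxicity that 11.1.2 does not contain. Point both to Table 1.
- **Order of actions.** State that the 3.1.1 hold is the immediate step and that Table 1 governs what follows for related events.
- **Blinding.** Table 1 speaks of holding the study drug, while 3.1.1 holds both creams. State that holds and once-daily reductions apply to both.

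The cost is one symbol and a few clarifying sentences in an amendment, with no added visits, procedures or patients.

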## 3.2 DRUG ADMINISTRATION

Topical ruxolitinib cream and vehicle cream will be supplied by Incyte in containers labeled with a perforated label as active study drug or placebo. The pharmacy will remove the perforated label and apply a label containing site of administration as well as label A or B according to the randomization table. Participants will be carefully instructed regarding the site of application of each cream. Neither the study drug nor the vehicle cream should be applied to areas of skin with ulceration. Participants will be provided with photographs of the body site to apply each cream as a guide at home for application. Application will be twice a day (12 hours apart) for 6 weeks.

**Abbreviated Title:** Topical ruxolitinib in cGVHD

**Version Date:** 01/25/2021

Application should occur at approximately the same time each day and at least 2 hours before showering/bathing. Participants should wear gloves when applying cream. A new pair of gloves should be used when applying cream to the second site. This will minimize the possibility of cross contamination. Medication and vehicle cream will be applied as a thin layer. Patients will be asked to complete a medication diary (APPENDIX G).

If a dose is missed, it should be applied as soon as possible on the same day unless it is within 1 hour of the next dose. If it is within 1 hour of the next dose, the missed dose should not be applied. Missed doses will not be reported to the IRB as a protocol deviation unless the patient misses > 5 doses per month.

During application of the study drug and the vehicle, care should be taken to avoid the eyes and mouth. If study drug or vehicle are ingested, study staff should be contacted immediately. If the cream is applied to the participant's body by a pregnant individual, that individual should use gloves and a wooden applicator to apply the creams on to the participant.

### 3.3 DOSE MODIFICATIONS

**Table 1: Dose Modifications**

All dose modifications will be discussed with the PI or MAI.

Adverse event	CTCAE grade/attribution	Protocol Action
Any adverse event (excluding ulceration, infection, treatment-related malignancy)	Grade 2 >7 days that is probably or definitely related to study drug.	Hold study drug; *If AE resolves to ≤ grade 1 or baseline within 7 days: resume dose. ** If AE does not resolve to ≤ grade 1 or baseline within 7 days: patient comes off drug.
Any adverse event (excluding ulceration, infection, treatment-related malignancy)	Same grade 2 >7 days recurs that is probably or definitely related to study drug.	Hold study drug; *If AE resolves to ≤ grade 1 or baseline within 7 days: decrease dose to once daily. **If AE does not resolve to ≤ grade 1 or baseline within 7 days: patient comes off drug.
Any adverse event (excluding ulceration, infection, treatment-related malignancy)	Same grade 2 >7 days recurs after dose reduction that is probably or definitely related to study drug.	Patient comes off drug.
Any adverse event (excluding ulceration,	Grade 3 that is probably or definitely related to study drug.	Hold study drug; *If AE resolves to ≤ grade 1 or baseline within 7 days:

**Abbreviated Title:** Topical ruxolitinib in cGVHD

**Version Date:** 01/25/2021

infection, treatment-related malignancy)		decrease dose to once daily. **If AE does not resolve to $\leq$ grade 1 or baseline within 7 days: patient comes off drug.
Any adverse event (excluding ulceration, infection, treatment-related malignancy)	Same grade 3 recurs after dose reduction that is probably or definitely related to study drug.	Patient comes off drug.
Any adverse event (excluding ulceration, infection, treatment-related malignancy)	Grade 4 that is probably or definitely related to study drug.	Patient comes off drug.
Skin ulceration at treatment site	Any grade	Patient comes off drug.
Infection	Grade 2 that is probably or definitely related to study drug.	Hold study drug until completion of systemic antibiotic course and resolution of infection, then restart at same dose level.
Infection	Grade 2 recurs that is probably or definitely related to study drug.	Hold study drug until completion of systemic antibiotic course and resolution of infection, then decrease dose to once daily.
Infection	Grade 2 recurs after dose reduction that is probably or definitely related to study drug.	Patient comes off drug.
Infection	Grade 3 that is probably or definitely related to study drug.	Patient comes off drug.
Infection	Grade 4	Patient comes off drug.
Treatment-related malignancy	Grade 3	Patient comes off drug.
Treatment-related malignancy	Grade 4	Patient comes off drug.

Exceptions to the above treatment modifications:

1. Alopecia any grade

**Abbreviated Title:** Topical ruxolitinib in cGVHD

**Version Date:** 01/25/2021

2. Dry skin any grade
3. Grade 2 skin or soft tissue infection at untreated site
4. Grade 2 paronychia

Doses withheld while recovering from an adverse event should not be made up.

### 3.4 QUESTIONNAIRES

The following scales will be administered twice at each indicated time point to independently assess the 2 treatment sites.

1. Pruritus Visual Analog Scale (VAS) is a self-administered psychometric response instrument which measures subjective characteristics or attitudes that cannot be directly measured. It ranges from 0-10. This scale has been used for measurement in a variety of dermatologic settings. This questionnaire will be administered at baseline, week 2, week 4 (for participants who come for an in-person study visit), and week 6. (1 minute)
2. Skin Pain VAS is a self-administered psychometric response instrument which measures subjective characteristics or attitudes that cannot be directly measured. It ranges from 0-10. This scale has been used for measurement in a variety of dermatologic settings. This questionnaire will be administered at baseline, week 2, week 4 (for participants who come for an in-person study visit), and week 6. (1 minute)
3. Overall Disease Severity VAS is a self-administered psychometric response instrument which measures subjective characteristics or attitudes that cannot be directly measured. It ranges from 0-10. This scale has been used for measurement in a variety of health settings. This questionnaire will be administered at baseline, week 2, week 4 (for participants who come for an in-person study visit), and week 6. (1 minute)

